Major Bleeding Event	Both VA and Medicare	Major bleeding event(s) observed during follow-up will be identified using hospital claims which had a MB diagnosis as the primary diagnosis code and occurring anytime during the follow-up period of drug use or within 30 days from the last day of supply of treatment prescription. A major bleeding event will be a dichotomous variable that equals 1 if there is ≥ 1 bleeding event during the follow-up period. Time to the first major bleeding event will be calculated. The first major bleeding event will be stratified by gastrointestinal (GI), intracranial hemorrhage (ICH), and other MB. (See Appendix Table 12 for codes).
Stroke/SE Event	Both VA and Medicare	Stroke/SE will be identified using hospital claims which had a stroke/SE diagnosis code as the primary diagnosis code and occurring anytime during the period of drug use or within 30 days from the last day of supply of treatment prescription. Stroke/SE will be a dichotomous variable that equals 1 if there is ≥ 1 stroke event during the follow-up period. Time to the first stroke/SE event will be calculated. The first stroke/SE event will be stratified by ischemic stroke, hemorrhagic stroke, and SE. (See Appendix Table 12 for codes).
Net Clinical Benefit	Both VA and Medicare	For patients with stroke/SE OR MB event, net clinical benefit will be assessed by evaluating the first hospital claim for a stroke/SE or MB event. The hospital claim can occur anytime during the period of drug use or within 30 days from the last day of supply of treatment prescription.
INR	VA	International Normalized Ratio Test Results will be identified using Logical Observation Identifiers Names and Codes (LOINC; 34714-6, 38875-1, 46418-0, 52129-4, 5895-7, 5896-5, 61189-7, 6301-6, 72281-9) occurring anytime during the period of drug use or within 30 days from the last day of supply of treatment prescription. The mean

Variable	Data Source(s)	Operational Definition
		and median number of INR tests for warfarin patients will be calculated. The distribution of INR values (mean, median, maximum, minimum, Q1, Q3) will be evaluated descriptively and flags will be created for INR <2, 2-3, and >3.

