9.5. Study Size

All eligible patients available for analysis will be included.

A feasibility analysis was conducted to examine the sample size of patients available in the linked VA and Medicare dataset with diagnosis of NVAf and BMI or body weight reported within ± 6 months of index diagnosis. Enrollment in Medicare Part D was removed as an inclusion criterion during the feasibility analysis as 50% of the study population would be excluded. Many patients in this study population use VA prescription drug benefits due to

cost savings over Medicare Part D. However, we will identify OAC use from Medicare Part D in patients who have this coverage along with VA pharmacy benefits. Approximately 56,000 patients would be included in this study population, with 20,000 included in the apixaban cohort. The VA feasibility study results and hazard ratios (HR) were used to calculate the needed sample size below.

A power calculation was completed for effectiveness outcomes comparing the difference between stroke rates using an alpha of 0.05, power of 80%, an accrual period of 4.5 years (identification period where patients are selected into the study), and a loss of follow-up of 55% for the warfarin cohort and 40% for the apixaban cohort. Using the stroke hazard ratio of 0.63 (from ARISTOPHANES Obesity subgroup²³ and an incidence rate of 1.10 per 100 person-years (from VA-Medicare feasibility analysis conducted in Q1-Q2 2020) in the warfarin group, a Cox proportional hazards analysis of stroke would need 7,945 patients per cohort (1:1 matching).

- **Accrual Period:** 4.5 years (identification period).
- **Loss of follow-up:** 55% for the warfarin cohort and 40% for the apixaban cohort.
- **Alpha:** 0.05.
- **Power:** 80%.

Table 3. Power Calculation

Hazard Ratio (HR) Apixaban vs Warfarin		Incidence Rates for Stroke/SE (per 100 person-years)		Stroke/SE Sample Size		
HR	Source	Rate (warfarin)	Source	Apixaban	Warfarin	Total
OBESITY						
0.63	ARISTOPHANES- Obesity subgroup ²³	1.80	ARISTOPHANES- Obesity subgroup	4,882	4,882	9,764
0.63	ARISTOPHANES- Obesity subgroup	1.10	VA Feasibility	7,945	7,945	15,890
0.76	Sandhu et al ¹⁹	1.28	Sandhu et al	17,769	17,769	35,538
0.76	Sandhu et al	1.10	VA Feasibility	20,646	20,646	41,292
SEVERE OBESITY						
0.72	ARISTOPHANES- Obesity subgroup	1.60	ARISTOPHANES- Obesity subgroup	10,195	10,195	20,390
0.72	ARISTOPHANES- Obesity subgroup	0.87	VA Feasibility	18,640	18,640	37,280

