9.7.1. Analysis Plan for Primary Objective

Baseline demographic and clinical factors such as age, sex, geographic region, baseline medications, and co-morbidities among NVAf patients initiating OAC will be summarized. Descriptive statistics, (ie, mean, standard deviation, median, and inter-quartile range for continuous variables and differences across treatments) will be compared using the Student's t-test or Wilcoxon rank sum test. Percentages for categorical and binary variables will be presented for all baseline patient characteristics and will be compared using the chi-square test or Fisher's Exact test.

The cumulative incidence rate for clinical outcomes (stroke/SE, MB, net clinical benefit) will be calculated. MB will be stratified by GI bleeding, ICH, and other bleeding; Stroke/SE will be stratified by hemorrhagic, ischemic, and systemic embolism. The incidence rate will be calculated as the number of patients who experience the event divided by the observed time at risk. The incidence rate will be calculated per 100 person-years.

Inverse Probability Treatment Weighting (IPTW)

Inverse probability treatment weighting (IPTW) will be used to balance patient characteristics when comparing outcomes among different cohorts. Three sets of IPTW will be conducted (all patients, obese patients, and severely obese patients). Depending on sample size, IPTW will also be conducted for the standard dose patients separately. In addition, the primary analysis will be conducted for apixaban vs warfarin and depending on the sample size, other OAC comparisons will be conducted.

IPTW uses propensity scores to obtain estimates of the average treatment effect. The propensity score will be calculated using a logistic model with treatment cohorts included in the model, using warfarin patients as the reference (ie, control cohort). The propensity score is defined as the probability of a patient receiving a certain treatment or not conditional on their observed baseline covariates (eg, age, gender, comorbidities, medications, etc.). The list of variables included in the logistic model will be based on clinical rationale. The propensity score acts as a balancing score between the cohorts. After calculating the propensity score, the distribution of the propensity scores will be reviewed. Each patient will be weighted by the inverse of the probability of their treatment option (weight=1/propensity score).

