Rheumatologic disease	710.0x-710.19; 710.4x-; 714.0x-714.29; 714.81; 725.xx	M05, M32, M33, M34, M06, M315, M351, M353, M360	1
Peptic ulcer disease	531.0x-531.79; 532.4x-532.79; 533.4x-533.79; 534.0x-534.79; 531.9x; 532.9x; 533.9x; 534.9x Modified to remove: 531.00, 531.01, 531.20, 531.21, 531.40, 531.41, 531.60, 531.61 532.40, 532.41, 532.60, 532.61 533.40, 533.41, 533.60, 533.61, 534.00, 534.01, 534.20, 534.21, 534.40, 534.41, 534.60, 534.61	K25, K26, K27, K28	1

Condition	ICD-9 Code(s)	ICD-10 Code(s)	Point
Mild liver disease	571.2x; 571.4x-571.69	B18, K73, K74, K700, K701, K702, K703, K709, K717, K713, K714, K715, K760, K762, K763, K764, K768, K769, Z944	1
Diabetes (mild to moderate)	250.0x-250.39, 250.7x	E100, E101, E106, E108, E109, E110, E111, E116, E118, E119, E120, E121, E126, E128, E129, E130, E131, E136, E138, E139, E140, E141, E146, E148, E149	1
Diabetes + complications	250.4x-250.69	E102, E103, E104, E105, E107, E112, E113, E114, E115, E117, E122, E123, E124, E125, E127, E132, E133, E134, E135, E137, E142, E143, E144, E145, E147	2
Hemiplegia or paraplegia	342.xx; 344.1x	G81, G82, G041, G114, G801, G802, G830, G831, G832, G833, G834, G839	2
Renal disease	582.xx; 583.0x-583.79; 585.xx-586.99; 588.xx	N18, N19, N052, N053, N054, N055, N056, N057, N250, I120, I131, N032, N033, N034, N035, N036, N037, Z490, Z491, Z492, Z940, Z992	2
Any malignancy, including lymphoma and leukemia	140.xx-172.99; 174.xx-195.99; 200.xx-208.99	C00, C01, C02, C03, C04, C05, C06, C07, C08, C09, C10, C11, C12, C13, C14, C15, C16, C17, C18, C19, C20, C21, C22, C23, C24, C25, C26, C30, C31, C32, C33, C34, C37, C38, C39, C40, C41, C43, C45, C46, C47, C48, C49, C50, C51, C52, C53, C54, C55, C56, C57, C58, C60, C61, C62, C63, C64, C65, C66, C67, C68, C69, C70, C71, C72, C73, C74, C75, C76, C81, C82, C83, C84, C85, C88, C90, C91, C92, C93, C94, C95, C96, C97	2
Moderate/severe liver disease	456.0x-456.29; 572.2x-572.89 Modified to remove: 456.0x, 456.20	K704, K711, K721, K729, K765, K766, K767, I850, I859, I864, I982	3
Metastatic solid tumor	196.xx-199.99	C77, C78, C79, C80	6
AIDS	042.xx-044.99	B20, B21, B22, B24	6

Table 11. Baseline Comorbidities

Covariates	ICD-9-CM/CPT/HCPCS Codes	ICD-10-CM Codes
History Stroke/SE	Same as the outcome stroke/SE (Table 12)	Same as the outcome stroke/SE (Table 12)
History of Bleeding	Same as the outcome major bleeding (Table 12)	Same as the outcome major bleeding (Table 12)

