Transient ischemic attack (TIA)	435.x	G458, G459, Z8673
Coronary artery disease	410.xx-414.xx	I200, I201, I208, I209, I2101, I2102, I2109, I2111, I2119, I2121, I2129, I213, I214, I220, I221, I222, I228, I229, I240, I241, I248, I249, I2510, I25110, I25111, I25118, I25119, I252, I253, I2541, I2542, I255, I256, I25700, I25701, I25708, I25709, I25710, I25711, I25718, I25719, I25720, I25721, I25728, I25729, I25730, I25731, I25738, I25739, I25750, I25751, I25758, I25759, I25760, I25761, I25768, I25769, I25790, I25791, I25798, I25799, I25810, I25811, I25812, I2582, I2583, I2584, I2589, I259
Anemia and coagulation defects	280.xx-286.xx	D50-D53, D55-D59, D60-D69,

Table 12. Clinical Outcomes

Outcome Variables		ICD-9-CM/Procedure Codes	ICD-10-CM Codes/Procedure Codes
Stoke/ SE	Hemorrhagic Stroke	430.xx-432.xx Cases will be excluded if traumatic brain injury (ICD-9: 800-804, 850-854) was present during hospitalization.	I6000, I6001, I6002, I6010, I6011, I6012, I602, I6030, I6031, I6032, I604, I6050, I6051, I6052, I606, I607, I608, I609, I610, I611, I612, I613, I614, I615, I616, I618, I619; Cases will be excluded according to Table 12.
	Ischemic Stroke	433.x1, 434.x1, 436	I6300, I63011, I63012, I63013, I63019, I6302, I63031, I63032, I63033, I63039, I6309, I6310, I63111, I63112, I63113, I63119, I6312, I63131, I63132, I63133, I63139, I6319, I6320, I63211, I63212, I63213, I63219, I6322, I63231, I63232, I63233, I63239, I6329, I6330, I63311, I63312, I63313, I63319, I63321, I63322, I63323, I63329, I63331, I63332, I63333, I63339, I63341, I63342, I63343, I63349, I6339, I6340, I63411, I63412, I63413, I63419, I63421, I63422, I63423, I63429, I63431, I63432, I63433, I63439, I63441, I63442, I63443, I63449, I6349, I6350, I63511, I63512, I63513, I63519, I63521, I63522, I63523, I63529, I63531, I63532, I63533, I63539, I63541, I63542, I63543, I63549, I6359, I636, I638, I639, I6789
	Systemic	444.x, 445.x	I7401, I7409, I7410, I7411, I7419, I742, I743,

Outcome Variables		ICD-9-CM/Procedure Codes	ICD-10-CM Codes/Procedure Codes
	Embolism		I744, I745, I748, I749, I75011, I75012, I75013, I75019, I75021, I75022, I75023, I75029, I7581, I7589

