Major Bleeding	Major Gastrointestinal bleeding event	456.0, 456.20, 530.82, 531.0x, 531.2x, 531.4x, 531.6x, 532.0x, 532.2x, 532.4x, 532.6x, 533.0x, 533.2x, 533.4x, 533.6x, 534.0x, 534.2x, 534.4x, 534.6x, 535.01, 535.11, 535.21, 535.31, 535.41, 535.51, 535.61, 537.83, 562.02, 562.03, 562.12, 562.13, 568.81, 569.3, 569.85, 578.x; Procedure Code: 44.43	I8501, I8511, K2211, K226, K250, K252, K254, K256, K260, K262, K264, K266, K270, K272, K274, K276, K280, K282, K284, K286, K2901, K2921, K2931, K2941, K2951, K2961, K2971, K2981, K2991, K31811, K3182, K5521, K5701, K5711, K5713, K5721, K5731, K5733, K5741, K5751, K5753, K5781, K5791, K5793, K625, K6381, K661, K920, K921, K922, K9161, K9162, K91840, K91841
	Major Intracranial Hemorrhage (ICH)	430, 431, 432.0, 432.1, 432.9, 852.0x, 852.2x, 852.4x, 853.0x	I6000, I6001, I6002, I6010, I6011, I6012, I602, I6030, I6031, I6032, I604, I6050, I6051, I6052, I606, I607, I608, I609, I610, I611, I612, I613, I614, I615, I616, I618, I619, I6200, I6201, I6202, I6203, I621, I629, S06340A, S06341A, S06342A, S06343A, S06344A, S06345A, S06346A, S06347A, S06348A, S06349A, S06350A, S06351A, S06352A, S06353A, S06354A, S06355A, S06356A, S06357A, S06358A, S06359A, S06360A, S06361A, S06362A, S06363A, S06364A, S06365A, S06366A, S06367A, S06368A, S06369A, S064X0A, S064X1A, S064X2A, S064X3A, S064X4A, S064X5A, S064X6A, S064X7A, S064X8A, S064X9A, S065X0A, S065X1A, S065X2A, S065X3A, S065X4A, S065X5A, S065X6A, S065X7A, S065X8A, S065X9A, S066X0A, S066X1A, S066X2A, S066X3A, S066X4A, S066X5A, S066X6A, S066X7A, S066X8A, S066X9A
	Major Other hemorrhage	285.1, 360.43, 362.43, 362.81, 363.61, 363.62, 363.72, 364.41, 372.72, 374.81, 376.32, 377.42, 379.23, 423.0x, 596.7x, 599.7x, 602.1x, 620.1, 621.4, 626.2, 626.5, 626.7, 626.8, 626.9, 719.1x, 782.7, 784.7, 784.8, 786.3x, 958.2, 997.02, 998.11; Procedure codes: 99.04	D62, D7801, D7802, D7821, D7822, E3601, E3602, E89810, E89811, G9731, G9732, G9751, G9752, H05231, H05232, H05233, H05239, H1130, H1131, H1132, H1133, H2100, H2101, H2102, H2103, H31301, H31302, H31303, H31309, H31311, H31312, H31313, H31319, H31411, H31412, H31413, H31419, H3560, H3561, H3562, H3563, H35731, H35732, H35733, H35739, H4310, H4311, H4312, H4313, H44811, H44812, H44813, H44819, H47021, H47022, H47023, H47029, H59111, H59112, H59113, H59119, H59121, H59122, H59123, H59129, H59311, H59312, H59313, H59319,

Outcome Variables	ICD-9-CM/Procedure Codes	ICD-10-CM Codes/Procedure Codes

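### Table 12 defines hemorrhagic stroke differently in ICD-9 and ICD-10: 432.xx counts but I62 does not, and the ICD-10 exclusion points to its own table without codes

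*Combined protocol and SAP*

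**What the plan says.** Section 9.3, Table 2 defines the outcome by code position: "Stroke/SE will be identified using hospital claims which had a stroke/SE diagnosis code as the primary diagnosis code". The codes are in Table 12 of Section 17.1. For hemorrhagic stroke the ICD-9 cell is "430.xx-432.xx Cases will be excluded if traumatic brain injury (ICD-9: 800-804, 850-854) was present during hospitalization". The ICD-10 cell lists I60 and I61 codes and ends "I618, I619; Cases will be excluded according to Table 12".

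The intracranial hemorrhage (ICH) row of Table 12, which feeds major bleeding, has an ICD-9 list that opens "430, 431, 432.0, 432.1, 432.9, 852.0x". Its ICD-10 list repeats the I60 and I61 codes and continues "I619, I6200, I6201, I6202, I6203, I621, I629, S06340A".

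Section 9.7.1 also reports the components: "Stroke/SE will be stratified by hemorrhagic, ischemic, and systemic embolism". In Table 11, the baseline history of stroke/SE takes its codes from the Table 12 outcome list.

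**The concern.** The study period is 2013 to 2017 and Table 12 supplies both code sets for it, so each outcome must mean the same thing under both. As written, stroke/SE does not. An admission in the 432/I62 category counts under ICD-9 and is dropped under ICD-10. The trauma exclusion has codes under ICD-9 and none under ICD-10.

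Stroke/SE is one of three outcomes named in Aims 2 and 3 and the only one in the power calculation (Section 9.5). If the drugs accrue person-time differently across the two coding eras, a change of definition can also enter the apixaban-warfarin comparison. The history of stroke/SE covariate inherits the mismatch, although a baseline I62 event would still be caught by history of bleeding.

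**Working it through.** The plan states no figure on this point, so the main check is a comparison of code lists. The arithmetic after it is illustrative.

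**1. Hemorrhagic stroke row against ICH row, Table 12**

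| | Hemorrhagic stroke | ICH, non-traumatic part |
|---|---|---|
| ICD-9 | 430.xx-432.xx | 430, 431, 432.0, 432.1, 432.9 |
| ICD-10 | 27 codes, I6000 to I619 | the same 27 plus I6200, I6201, I6202, I6203, I621, I629 (33 codes) |

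The ICD-10 lists differ by exactly those six I62 codes (33 − 27 = 6). No hemorrhagic stroke code is missing from the ICH list.

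**2. The ICD-10 exclusion.** Table 12 is the last table in the document. It contains no ICD-10 exclusion codes; its S06 codes are inclusions for ICH. The cell does not mention trauma, so reading it as the counterpart of the ICD-9 exclusion is an inference. On that reading it matters only for stays with a primary I60 or I61 diagnosis and an accompanying trauma code. Missing I62 codes lower the ICD-10 count, and an unapplied exclusion raises it.

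**3. Which outcomes are touched.** Stroke/SE and its hemorrhagic stratum are. Major bleeding is not, because the ICH row includes I62 and carries no trauma exclusion. Net clinical benefit is not, because I60-I62 and their ICD-9 counterparts all count through the ICH row.

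**4. Size.** Assumptions, none of them in the documents: fA and fW are the shares of 432-type events among ICD-9-era stroke/SE on apixaban and warfarin; pA and pW are the ICD-9-era shares of person-time; true rates are the same in both eras.

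*Rates.* The ICD-10-era stroke/SE rate is multiplied by 1 − f. Taking the "incidence rate of 1.10 per 100 person-years" of Section 9.5 only as a scale:
- f = 2%: 1.10 × 0.98 = 1.078
- f = 5%: 1.10 × 0.95 = 1.045
- f = 10%: 1.10 × 0.90 = 0.990

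If hemorrhagic stroke is an assumed share s = 15-25% of stroke/SE, its ICD-10-era rate falls by f/s. At f = 5% this is 0.05/0.15 = 33% to 0.05/0.25 = 20%. Over f = 2-10% it runs from 0.02/0.25 = 8% to 0.10/0.15 = 67%.

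*Hazard ratio.* Each drug's observed rate is the true rate times 1 − (1 − p)f, so the HR is multiplied by

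[1 − (1 − pA)fA] / [1 − (1 − pW)fW].

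| fA, fW | pA/pW = 50/50% | 40/60% | 20/70% |
|---|---|---|---|
| 5%, 5% | 1.000 | 0.970/0.980 = 0.990 | 0.960/0.985 = 0.975 |
| 2%, 5% | 0.990/0.975 = 1.015 | 0.988/0.980 = 1.008 | 0.984/0.985 = 0.999 |
| 5%, 2% | 0.975/0.990 = 0.985 | 0.970/0.992 = 0.978 | 0.960/0.994 = 0.966 |

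The range is 0.966 to 1.015, so a true 0.63 reads 0.608 to 0.640. Allowing 10% as well, the extremes are 0.920/0.994 = 0.926 and 0.990/0.950 = 1.042 (0.583 to 0.657).

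The factor is below 1 only if (1 − pA)fA > (1 − pW)fW. The sign therefore flips when fW/fA exceeds 0.5/0.5 = 1.0, 0.6/0.4 = 1.5 or 0.8/0.3 = 2.67 for the three splits. Later uptake of apixaban does not by itself fix the direction.

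*Against sampling error.* At HR 0.63, two-sided alpha 0.05 and 80% power, events = 4(1.960 + 0.842)²/(ln 0.63)² ≈ 147. The 95% CI half-width on the log scale is 1.96 × 2/√147 = 0.323. The factors 0.966 and 1.015 are 0.11 and 0.05 of that.

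The trauma gap is not quantified; the documents give nothing to base it on.

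**The case against.** The strongest reply is about reach. Two of the three primary outcomes are untouched by either gap, which is correct. Table 12 Cox models are planned for stroke/SE overall, while the hemorrhagic stratum is planned as a rate. Year of index OAC is a baseline variable in Table 1, and Section 9.7.1 gives its propensity covariates only as examples, checks balance after weighting and puts unbalanced variables into the Cox model. If index year is included, the two person-time splits should move closer. At 50/50% the factor for shares of 2-5% narrows to 0.985-1.015, and it is exactly 1 when fA = fW. That could reduce bias in the hazard ratio, though unequal follow-up could leave some. It cannot repair rates that change definition between eras.

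It can also be said that Table 12 does hold some ICD-10 trauma codes: the ICH row sets 852 and 853 codes beside S06 codes. But these are listed as inclusions and cover only part of 800-804 and 850-854, so a programmer still has no usable rule.

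Leaving out I62 may have been deliberate. In that case 432.xx should not be in the ICD-9 cell. Finally, Section 9.8 promises a clinical review of the coding strategy, but no item in its checklist compares definitions or event rates between code sets.

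**Conclusion.** The point holds and should be fixed. Following Table 12 exactly gives stroke/SE and its hemorrhagic stratum two definitions within one study, and this is shown by the table alone. The self-referring exclusion taken alone would be closer to missing detail; the 432/I62 mismatch carries the point.

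The effect on the apixaban-warfarin hazard ratio is probably small and its direction cannot be determined: a factor of 0.966 to 1.015 under assumed 2-5% shares, at most about 11% of the confidence-interval half-width. The hemorrhagic rate is more exposed, but the size of its fall depends entirely on assumed shares. Table 3 takes its rates as given, so no sample size changes.

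**What to change.** Use one hemorrhagic stroke definition under both code sets: either add I6200-I6203, I621 and I629 to the ICD-10 cell, or remove 432.xx from the ICD-9 cell. Replace the reference to Table 12 with an explicit ICD-10 traumatic brain injury list matching 800-804 and 850-854. Then check stroke/SE and hemorrhagic stroke rates by coding era.

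Two peripheral items can be settled in the same pass:
- For the same ICD-9 stroke range (V12.54, 433-436), Table 7 lists G450-G452, G458-G459, G460-G462, I67841, I67848 and Z8673, while Tables 5 and 6 do not. Reconcile the three tables. The separate TIA covariate in Table 11 already covers G458, G459 and Z8673.
- Table 10 removes codes from the cerebrovascular, peptic ulcer and moderate/severe liver rows in ICD-9 only. Carry the three deletions into the ICD-10 column.

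The cost is code-list editing in the appendix before programming, with no extra data.

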9. RESEARCH METHODS

9.1. Study Design

9.1.1. Key Index Period Definitions

[figure not shown]
- **Study Period:** The study period will range from January 1, 2013 through December 31, 2017.
- **Patient Identification Period:** The identification period will range from July 1, 2013 until December 31, 2017, allowing for a 6-month baseline period prior to the index date.
- **Baseline Period:** The baseline period will be 6 months prior to, and on, the index date.
- **Follow-up Period:** The follow-up period will be defined as the time period between the day after the index date and end of study period (December 31, 2017). Patients will be followed from the day after the index date to 30 days after the date of discontinuation, switch, death, end of study period, or end of continuous medical enrollment (Parts A & B), whichever is earlier.

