		H59321, H59322, H59323, H59329, H9521, H9522, H9541, H9542, I312, I97410, I97411, I97418, I9742, I97610, I97611, I97618, I97620, J9561, J9562, J95830, J95831, L7601, L7602, L7621, L7622, M2500, M25011, M25012, M25019, M25021, M25022, M25029, M25031, M25032, M25039, M25041, M25042, M25049, M25051, M25052, M25059, M25061, M25062, M25069, M25071, M25072, M25073, M25074, M25075, M25076, M2508, M96810, M96811, M96830, M96831, N421, N857, N897, N920, N923, N930, N938, N939, N9961, N9962, N99820, N99821, R040, R041, R042, R0489, R049, R233, R310, R319, R58, T792XXA; Procedure codes: 30230N1, 30230P1, 30233N1, 30233P1, 30240N1, 30240P1, 30243N1, 30243P1, 30250N1, 30250P1, 30253N1, 30253P1, 30260N1, 30260P1, 30263N1, 30263P1

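### Table 12's ICD-9 and ICD-10 major-bleeding lists are not equivalent, so the case definition changes at the coding switch

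*Combined protocol and SAP*

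**What the plan says.** Section 9.1.1 sets the window: "The study period will range from January 1, 2013 through December 31, 2017". Table 2 in Section 9.3 identifies major bleeding from "hospital claims which had a MB diagnosis as the primary diagnosis code". The qualifying codes are in Table 12, in parallel ICD-9 and ICD-10 columns for gastrointestinal, intracranial and other hemorrhage.

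The ICD-9 gastrointestinal list begins "456.0, 456.20, 530.82, 531.0x, 531.2x, 531.4x, 531.6x" and ends its diagnosis codes with "537.83, 562.02, 562.03, 562.12, 562.13, 568.81, 569.3, 569.85, 578.x". The ICD-10 list begins "I8501, I8511, K2211, K226, K250, K252, K254, K256" and later includes "K2991, K31811, K3182, K5521". The ICD-10 list for other hemorrhage closes its diagnosis codes with "R310, R319, R58, T792XXA".

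Net clinical benefit (Table 2) is the first hospital claim for stroke/SE or major bleeding. Table 11 defines history of bleeding by the same Table 12 list. Section 9.7.1 reports outcomes as incidence rates per 100 person-years as well as hazard ratios.

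**The concern.** When an outcome is built from two code systems, each lesion should count under both or under neither. Here several hemorrhage diagnoses qualify under one system only. An admission can then be an event or a non-event according to the code system in force on its date.

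Major bleeding is one of the three outcomes named in Aims 2 and 3 and is a component of net clinical benefit. A rate pooled over the whole window would mix two definitions. The mismatch also reaches baseline data through history of bleeding, and through the HAS-BLED bleeding item. Table 7 points that item to Table 12 on the ICD-9 side, while its own ICD-10 list again includes K2211, K226, K3182, K6381 and R58.

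**Working it through.** **1. Inputs.** Whether a code is listed can be read directly from Table 12. Which ICD-9 code corresponds to which ICD-10 code is an assumption taken from the standard code sets, because the documents contain no crosswalk. They also give no switch date; 1 October 2015 is assumed as the US date.

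**2. ICD-10 entries checked against the ICD-9 side**, with each x wildcard expanded:

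| Listed in ICD-10 | Standard ICD-9 counterpart | In any ICD-9 major-bleeding row? |
|---|---|---|
| K2211 (esophageal ulcer with bleeding) | 530.21 | No; the only 530 code is 530.82 |
| K226 (gastro-esophageal laceration-hemorrhage) | 530.7 | No; same reason |
| K3182 (Dieulafoy lesion, stomach or duodenum) | 537.84 | No; the only 537 code is 537.83 |
| K6381 (Dieulafoy lesion, intestine) | 569.86 | No; the 569 block has 569.3 and 569.85 only |
| R58 (hemorrhage not elsewhere classified) | 459.0 | No |

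The stomach part of the ICD-9 list shows the gap plainly: "535.51, 535.61, 537.83, 562.02, 562.03, 562.12, 562.13" goes from 537.83 straight to the 562 block.

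Control pairs are present on both sides: K31811/537.83, K5521/569.85, K625/569.3, K661/568.81, I312/423.0x and N421/602.1x. The lists are therefore meant to be parallel, and the gaps look like omissions rather than a rule.

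**3. ICD-9 entries checked against the ICD-10 side.** Five have no evident partner: 530.82 in the gastrointestinal row, and 374.81, 596.7x, 620.1 and 997.02 in the other-hemorrhage row. For these the bleed counts before the switch and not after it.

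**4. Illustrative effect on the hazard ratio.** The plan states no figure to reproduce. Let f be the extra bleeds counted only under ICD-10 and g those counted only under ICD-9, each as a share of bleeds counted under both. Let pA and pW be the shares of apixaban and warfarin person-time in the ICD-10 era. With equal f and g in both arms, constant true rates and no calendar adjustment:

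factor on HR = [1 + f·pA + g·(1 − pA)] / [1 + f·pW + g·(1 − pW)]

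All four inputs are assumed. Section 7 says DOACs were increasingly preferred over warfarin, which makes pA > pW plausible but does not quantify it.

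| Share | f only, pA/pW = 0.6/0.5 | f only, 0.9/0.3 | g only, 0.6/0.5 | g only, 0.9/0.3 |
|---|---|---|---|---|
| 1% | 1.006/1.005 = 1.001 | 1.009/1.003 = 1.006 | 1.004/1.005 = 0.999 | 1.001/1.007 = 0.994 |
| 5% | 1.030/1.025 = 1.005 | 1.045/1.015 = 1.030 | 1.020/1.025 = 0.995 | 1.005/1.035 = 0.971 |
| 10% | 1.060/1.050 = 1.010 | 1.090/1.030 = 1.058 | 1.040/1.050 = 0.990 | 1.010/1.070 = 0.944 |

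If f = g the factor is exactly 1. The sign depends on which share is larger, and the documents do not say.

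**5. Absolute rates.** With g = 0, the counted rate steps up by a factor of 1 + f at the switch, that is by 1-10% over the assumed range. With f = 0 it steps down by a factor of 1/(1 + g).

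**The case against.** A reader might infer that bleeds are simply under-counted in the ICD-9 years and that apixaban, used later, is therefore charged with more bleeds for the same risk. The documents do not support this. At least five entries run the other way, nothing gives the frequency of any code, and no person-time by era is reported. A one-directional result appears only if the ICD-9-only codes are left out of the calculation.

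Nor can one say that every such admission in the early years is lost. Some may have been coded to 578.x, which is listed. Table 12 also lists procedure codes (44.43, 99.04), and Table 2 does not say whether a procedure code alone qualifies.

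The plan also has a partial safeguard. Year of index OAC is a Table 1 baseline variable. Section 9.7.1 checks balance after weighting against a 10% standardized difference and puts unbalanced variables into the Cox model. If index year is handled this way, much of the era imbalance would leave the hazard ratio. This is not guaranteed: the propensity variables are left to clinical rationale, and index year is not among the named examples. On the assumed switch date, a yearly flag would also not separate the two eras within 2015. And balancing index year does nothing for the absolute rates.

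Section 9.8 promises a clinical review of the coding strategy. That is a natural place for the check, but it names no crosswalk.

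The code pairings do come from outside the documents. That limits certainty about individual pairs, but not the visible fact that the two lists differ.

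**Conclusion.** The point holds as a defect in the case definition. Five ICD-10 hemorrhage entries lack their standard ICD-9 counterparts, and five ICD-9 entries have no evident ICD-10 counterpart. What counts as major bleeding therefore changes at the coding switch. The major-bleeding and net-clinical-benefit rates and the history-of-bleeding covariate are affected.

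It does not establish a bias for or against apixaban. The net direction and size of any effect on the hazard ratio cannot be determined from the documents. The assumed range of 0.944 to 1.058 has its extremes at a 10% one-sided mismatch combined with a 0.9 versus 0.3 split of person-time and no calendar adjustment. At 5% or less it is 0.971 to 1.030. The effect is probably small. The case for acting rests on the importance of the outcome and the ease of the correction. The conclusion assumes the standard code pairings.

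**What to change.** Before outcomes are extracted:

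- Add 530.21, 530.7, 537.84, 569.86 and 459.0 to the ICD-9 major-bleeding lists, or remove K2211, K226, K3182, K6381 and R58 from the ICD-10 lists. Record which choice was made and why.
- Run both columns through a documented crosswalk, and for 530.82, 374.81, 596.7x, 620.1 and 997.02 either find a bleed-specific ICD-10 partner or drop or justify the entry. Do not add K22.8 by default as the partner of 530.82: nothing in the documents shows that it is specific to bleeding.
- Carry the aligned list into history of bleeding (Table 11) and the HAS-BLED bleeding item (Table 7).

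The cost is a code-list edit before programming, and possibly less comparability with any earlier study that used the same list.
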